## **Sodium Chloride for Injection, 0.9% (normal saline, Sodium Chloride for Injection, 0.9%)**

Sodium Chloride for Injection, 0.9% will be used for the Bivalent Subtype C gp120 alone group to maintain blinding between the groups. It must be stored as directed by the manufacturer.

### **8.3 Preparation of study products**

Pharmacists should refer to USP 38 General Chapter Physical Tests / <797> Pharmaceutical Compounding - Sterile, and should follow the requirements of their country, their institution, and their pharmacy regulatory authority regarding these procedures. At a minimum, study products must be prepared in a biological safety cabinet/isolator by appropriately trained/qualified pharmacy personnel using aseptic technique.

#### **8.3.1 ALVAC-HIV (vCP2438) (All Groups)**

One vial of ALVAC-HIV (vCP2438) and 2 vials of diluent (NaCl 0.4%) are needed to prepare this dose.

Before reconstitution, the pharmacist will allow the vials to equilibrate to room temperature. The pharmacist, using aseptic technique, will withdraw a total of 1 mL from the 2 vials containing diluent (NaCl 0.4%) and slowly inject (the 1 mL of diluent) into the vial containing the lyophilized ALVAC-HIV. The pharmacist will then set the vial aside and allow the vial to sit for up to 3 minutes to allow for dissolution of the vaccine. The pharmacist will gently swirl the vial to assure the contents are well dissolved. DO NOT SHAKE THE VIAL. (Note: Presence of particles or filaments in the dissolved solution is possible). Using aseptic technique, the pharmacist will then withdraw the total contents of the ALVAC-HIV vial into a 2, 3 or 5 mL syringe.

The syringe should be labeled as “ALVAC-HIV 1 mL” as well as “Administer in Left Deltoid”. Once the dose is drawn up in a syringe, the study product should be administered as soon as possible within 30 minutes (per Immunization Action Coalition [IAC] and US Centers for Disease Control and Prevention [CDC] recommendations).

Any unused portion of reconstituted vials or expired syringes are disposed of in accordance with institutional or pharmacy policy for a biological safety level 1 product.

#### **8.3.2 Bivalent Subtype C gp120/MF59® (Groups 1 and 3)**

One vial of TV1.C gp120 protein, 1 vial of 1086.C gp120 protein, and 1 vial of MF59C.1 will be needed to prepare the dose. Prior to dispensing, the pharmacist will remove the TV1.C gp120 and 1086.C gp120 from the freezer and allow to thaw at room temperature. (Note: Once thawed the 1086.C gp120 and/or TV1.C gp120 vials should be used immediately for preparation or stored in a refrigerator at 2-8°C for no longer than 24 hours. Unused 1086.C gp120 and/or TV1.C gp120 protein vials should be quarantined for destruction after this time.) The pharmacist will also remove the MF59C.1 vial from the refrigerator and mix by repeated gentle swirling and inversion (do not shake vigorously).

Using aseptic technique, the pharmacist will gently swirl the contents of the vial containing TV1.C gp120 and then withdraw 0.35 mL of TV1.C gp120 from the correct vial and inject it into the vial containing MF59C.1. The pharmacist will then gently swirl the vial containing 1086.C gp120 after which, using aseptic technique, the pharmacist will withdraw 0.35 mL of 1086.C gp120 from the correct vial and inject it into the MF59C.1 vial (which contains TV1.C gp120 and MF59C.1). After gentle swirling and inversion (do not shake vigorously) the pharmacist, using aseptic technique, will withdraw 0.5 mL of the mixed preparation for dosing into a 1 or 2 mL syringe.

The syringe should be labeled as “HVTN 107 study product” and have an overlay applied to the syringe. Although Group 3 is not blinded, this will maintain consistency with the other groups. The syringe must also be labeled for administration in RIGHT deltoid and “Gently roll the syringe prior to administration”. The syringe containing study product should be bagged for transport to the clinic where it will be administered. This study product should be administered immediately, defined as within 30 minutes as per IAC recommendations. If this is not possible, the vaccine should be stored at 2°C-8°C until administration and if not used within 2 hours, it should be discarded.

### **8.3.3 Bivalent Subtype C gp120 admixed with Aluminum Hydroxide Suspension (Group 2)**

One vial of TV1.C gp120 protein, 1 vial of 1086.C gp120 protein, 1 vial of Aluminum Hydroxide Suspension, 1 vial/ampule of Sterile Water for Injection, and 1 empty sterilized vial will be needed to prepare the dose. Prior to dispensing, the pharmacist will remove the TV1.C gp120 and 1086.C gp120 from the freezer and allow to thaw at room temperature. (Note: Once thawed the 1086.C gp120 and/or TV1.C gp120 vials should be used immediately for preparation or stored in a refrigerator at 2-8°C for no longer than 24 hours. Unused 1086.C gp120 and/or TV1.C gp120 protein vials should be quarantined for destruction after this time.) The pharmacist will also remove the Aluminum Hydroxide Suspension vial from the refrigerator and the Sterile Water for Injection from storage.

Using aseptic technique, the pharmacist will gently swirl the contents of the vial containing aluminum hydroxide, withdraw 0.35 mL of the aluminum hydroxide and inject it into the empty sterilized vial. The pharmacist will then add 0.35 mL of Sterile Water for Injection to the mixing vial which contains the 0.35 mL of aluminum hydroxide. The mixing vial should be gently swirled and inverted (do not shake). Next, the pharmacist will take the vial containing TV1.C gp120 and withdraw 0.35 mL of TV1.C gp120 from the vial and inject it into the mixing vial (which contains aluminum hydroxide mixed with Sterile Water for Injection). The pharmacist will then gently swirl the vial containing 1086.C gp120 after which, using aseptic technique, the pharmacist will withdraw 0.35 mL of 1086.C gp120 from the correct vial and inject it into the mixing vial (which contains TV1.C gp120 and aluminum hydroxide mixed with Sterile Water for Injection). After gentle swirling and inversion (do not shake vigorously) the pharmacist, using aseptic technique, will withdraw 0.5 mL of the mixed preparation for dosing into a 1 or 2 mL syringe.

The syringe should be labeled as “HVTN 107 study product” and have an overlay applied to the syringe. The syringe must also be labeled for administration in RIGHT deltoid and “Gently roll the syringe prior to administration”. The syringe containing study product should be bagged for transport to the clinic where it will be administered. This study product should be administered immediately, defined as within 30 minutes as per IAC

recommendations. If this is not possible, the vaccine should be stored at 2°C-8°C until administration and if not used within 2 hours, it should be discarded.

#### **8.3.4 Bivalent Subtype C gp120 (Group 4)**

One vial of TV1.C gp120 protein, 1 vial of 1086.C gp120 protein, Sodium Chloride for Injection, 0.9%, and 1 empty sterilized vial will be needed to prepare the dose. Prior to dispensing, the pharmacist will remove the TV1.C gp120 and 1086.C gp120 from the freezer and allow to thaw at room temperature. (Note: Once thawed the 1086.C gp120 and/or TV1.C gp120 vials should be used immediately for preparation or stored in a refrigerator at 2-8°C for no longer than 24 hours. Unused 1086.C gp120 and/or TV1.C gp120 protein vials should be quarantined for destruction after this time.)

The pharmacist will also obtain the sodium chloride for injection and 1 empty sterilized vial from storage.

Using aseptic technique, the pharmacist will transfer 0.7 mL of Sodium Chloride for Injection in to the empty sterilized vial. The pharmacist will then gently swirl the contents of the vial containing TV1.C gp120 and withdraw 0.35 mL of TV1.C gp120 from the correct vial and inject it into the mixing vial containing the sodium chloride for injection. The pharmacist will then gently swirl the vial containing 1086.C gp120 after which, using aseptic technique, the pharmacist will withdraw 0.35 mL of 1086.C gp120 from the correct vial and inject it into the mixing vial (which contains TV1.C gp120 and sodium chloride for injection). After gentle swirling and inversion (do not shake vigorously) the pharmacist, using aseptic technique, will withdraw 0.5 mL of the mixed preparation for dosing into a 1 or 2 mL syringe.

The syringe should be labeled as “HVTN 107 study product” and have an overlay applied to the syringe. The syringe must also be labeled for administration in RIGHT deltoid and “Gently roll the syringe prior to administration”. The syringe containing study product should be bagged for transport to the clinic where it will be administered. This study product should be administered immediately, defined as within 30 minutes as per IAC recommendations. If this is not possible, the vaccine should be stored at 2°C-8°C until administration and if not used within 2 hours, it should be discarded.

### **8.4 Administration**

All injections are to be given IM in the deltoid indicated. At sites where registered pharmacists are legally authorized to administer injections, the HVTN CRS may choose to have the pharmacist administer vaccinations.

When preparing a dose in a syringe and administering the dose, consideration should be given to the volume of solution in the needle before and after the dose is administered. Particularly, if the needle used to withdraw the product is replaced prior to vaccine administration, consideration should be given to conserving the full dose of product. The pharmacy and clinic staff members are encouraged to work together to administer the dose specified in the protocol.

All injections are to be given using standard IM injection technique.

For all syringes containing Bivalent Subtype C gp120 with or without adjuvant, the person administering the injection should gently roll the syringe prior to administration of the study product. These syringes will be labeled as “HVTN 107 study product”.

If an injection is administered in the contralateral deltoid due to a medical contraindication, the appropriate study staff should document this clearly. Under this circumstance, this is NOT a protocol violation. Two injections administered into the same deltoid should be at least 2.4 cm apart and should be documented in the participant’s study record.

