## 4.8 Trial design rationale

The primary objective of the study is to compare the humoral immune responses induced by the MF59®- and alum-adjuvanted vaccine regimens; while the unadjuvanted group is included to provide information about the added value of the adjuvants. Therefore, a smaller sample size for the unadjuvanted controls is sufficient. Other important questions to be answered in this study are to compare the quality, magnitude, kinetics, and duration of the humoral and T-cell responses depending on the adjuvant used or whether ALVAC and proteins are co-administered during early vaccinations. The subset of participants who will provide innate immunity and mucosal samples will include 18 participants from each of the vaccine regimens.

Group assignments are randomized to provide unbiased estimates of the safety and immunogenicity parameters of the different study arms. In addition, Groups 1, 2, and 4 are double blinded to study arm assignment. Because Group 3 has a different vaccination schedule and because blood draws for innate immunity assays occur at different timepoints from the other 3 groups in the trial, it would not be possible to include Group 3 in the blind without imposing an excessive number of unnecessary clinic visits, placebo injections, and (possibly) invasive study procedures on all trial participants. For this reason, a decision was taken to not include Group 3 in the blind.

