## 5 Objectives and endpoints

### 5.1 Primary objectives and endpoints

*Primary objective 1:*

To compare the humoral immune responses induced by ALVAC-HIV (vCP2438) prime with 2 ALVAC-HIV (vCP2438) + Bivalent Subtype C gp120/MF59® boosts or 2 ALVAC-HIV (vCP2438) + Bivalent Subtype C gp120 admixed with Aluminum Hydroxide Suspension boosts in HIV-uninfected participants

*Primary endpoint 1:*

Occurrence and level of vaccine-induced systemic IgG Ab binding to the 3 gp120 Env proteins contained in the vaccine regimen (ZM96, TV1.C, and 1086.C) at the Month 6.5 timepoint

*Primary objective 2:*

To compare the humoral immune responses induced by ALVAC-HIV (vCP2438) prime with 2 ALVAC-HIV (vCP2438) + Bivalent Subtype C gp120/MF59® boosts to the regimen with 3 ALVAC-HIV (vCP2438) + Bivalent Subtype C /MF59® vaccinations in HIV-uninfected participants

*Primary endpoint 2:*

Occurrence and level of vaccine-induced serum IgA Ab binding to the 3 gp120 Env proteins contained in the vaccine regimen (ZM96, TV1.C, and 1086.C) at the Month 6.5 timepoint

*Primary objective 3:*

To evaluate the safety and tolerability of each vaccine regimen through the Month 6.5 timepoint

*Primary endpoint 3:*

Severe local and systemic reactogenicity signs and symptoms (pain, tenderness, erythema, induration, fever, malaise/fatigue, myalgia, headache, nausea, vomiting, chills, arthralgia) within 3 days after each vaccine dose

AEs by body system, Medical Dictionary for Regulatory Activities (MedDRA) preferred term, severity, and assessed relationship to study products within 30 days after each vaccine dose

SAEs, AEs of special interest (AESIs), and new chronic conditions requiring medical intervention for  $\geq$  30 days, throughout the study

Laboratory measures: white blood cells (WBC), neutrophils, lymphocytes, hemoglobin, platelets, alanine aminotransferase (ALT), aspartate aminotransferase (AST), alkaline phosphate (ALP), and creatinine at baseline and following vaccinations

AEs leading to early participant withdrawal or early discontinuation of study product(s) administration throughout the study

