## 6.2 Randomization

The randomization sequence will be obtained by computer-generated random numbers and provided to each HVTN CRS through the SDMC's Web-based randomization system. The randomization for the subset and non-subset portion of the trial will each be done in blocks to ensure balance across arms and stratified by country. At each institution, the pharmacist with primary responsibility for dispensing study products is charged with maintaining security of the treatment assignments.

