## 6.3 Blinding

Participants and site staff (except for site pharmacists) will be blinded as to participant treatment group assignments for the 3 heterologous prime boost arms of the study (Groups 1, 2, 4); the ALVAC + Bivalent Subtype C gp120 adjuvanted with MF59 at all vaccination time points will not be blinded (Group 3). Study product assignments are accessible to those HVTN CRS pharmacists, DAIDS protocol pharmacists and contract monitors, and SDMC staff who are required to know this information in order to ensure proper trial conduct. Any discussion of study product assignment between pharmacy staff and any other HVTN CRS staff is prohibited. The HVTN SMB members also are unblinded to treatment assignment in order to conduct review of trial safety.

When a participant leaves the trial prior to study completion, the participant will be told he or she must wait until all participants are unblinded to learn his or her treatment assignment (if he or she is in a blinded arm of the study).

Emergency unblinding decisions will be made by the site investigator. If time permits, the HVTN 107 PSRT should be consulted before emergency unblinding occurs.

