## **8.6 Pharmacy records**

The HVTN CRS pharmacist is required to maintain complete records of all study products. The pharmacist of record is responsible for maintaining randomization codes and randomization confirmation notices for each participant in a secure manner.

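### Section 8.4 lets a site's unblinded pharmacist inject participants in the double-blind groups: an avoidable risk of cueing self-reported reactogenicity, not a breach of the stated blind

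*Combined protocol and SAP*

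**What the plan says.** Section 4.8 states that "Groups 1, 2, and 4 are double blinded to study arm assignment"; Group 3 is open-label. Section 6.3 defines the blind for those three groups: "Participants and site staff (except for site pharmacists) will be blinded as to participant treatment group assignments". It adds a communication rule: "Any discussion of study product assignment between pharmacy staff and any other HVTN CRS staff is prohibited".

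The pharmacist knows the product in two ways. Sections 8.3.2 to 8.3.4 have the pharmacist mix the protein with MF59, with alum or with saline. On custody of the codes, Section 8.6 says: "The pharmacist of record is responsible for maintaining randomization codes and randomization confirmation notices for each participant in a secure manner". Section 6.2 adds that "the pharmacist with primary responsibility for dispensing study products is charged with maintaining security of the treatment assignments".

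The protein syringes carry a common study-product label and must "have an overlay applied to the syringe" (Section 8.3.4, with the same step in 8.3.2 and 8.3.3).

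Section 8.4 then says: "At sites where registered pharmacists are legally authorized to administer injections, the HVTN CRS may choose to have the pharmacist administer vaccinations". It does not limit this to Group 3, or to a pharmacist without access to assignments.

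Primary endpoint 3 (Section 5.1) begins with "Severe local and systemic reactogenicity signs and symptoms" in the three days after each dose.

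**The concern.** The protocol takes trouble to hide the adjuvant. It uses a saline mixture in Group 4 to preserve masking, an overlay on the syringe, and a wall between pharmacy and clinic. Section 8.4 allows the one member of site staff who sits outside the blind to meet the participant at the moment of injection.

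Reactogenicity depends heavily on what participants say. Section 9.10 collects it through daily contact with the site, and Section 6.4.3.1 compares severity between arms with Kruskal-Wallis tests. If someone who expects more reaction from one product signals that, by word or manner, the MF59, alum and no-adjuvant comparison of symptoms could be shifted. That comparison is the one at stake. Laboratory-measured IgG and IgA binding is not.

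**Working it through.** No figure in the plan depends on this point, so there is nothing to reproduce. The check compares the relevant sections and then counts the exposure.

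**1. Who knows the assignment.** Section 6.3 excepts site pharmacists as a class. The point therefore does not need the injector to be the pharmacist of record who keeps the codes under Section 8.6.

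**2. What each safeguard covers.**
- Label and overlay (8.3.2 to 8.3.4): mask the product from a participant or a blinded injector, but not from the person who mixed it.
- Discussion ban (6.3): covers pharmacy staff talking to other site staff. Participants are not mentioned.
- Duty to keep assignments secure (6.2): has no limit on audience, so it forbids telling a participant. It does not separate the roles, and it is a weak guard against unintended cues.
- Assessor (Table 9-1): the 25 to 60 minute assessment is done by site staff, later ones by site staff or the participant. Section 6.3 counts pharmacy staff among site staff, so nothing bars the injecting pharmacist from assessing.

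**3. How far the endpoint depends on self-report.** Primary endpoint 3 lists 12 signs and symptoms. Footnote b of Table 11-1 classes 8 of these as subjective: pain, tenderness, malaise/fatigue, myalgia, arthralgia, chills, headache and nausea.

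**4. Upper bound on exposure (Table 3-1, full enrolment, all doses given, every site using the option).**
- Blinded participants: 36 + 36 + 24 = 96 of 132 (72.7%).
- All three groups receive ALVAC alone at Months 0 and 1. The arm-specific injections are the protein doses at Months 3, 6 and 12.
- Within primary objective 3 (through Month 6.5): 96 × 2 = 192.
- With Month 12, which falls under secondary objective 2: 96 × 3 = 288. Section 6.4.3.1 takes each participant's maximum severity over all injection visits, so Month 12 enters the final tabulation.

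**5. Possible effect (assumed inputs only).** Let a share s of an arm be at sites using the option, and let cueing move the report rate by d. The arm's rate then moves by s × d. The documents give neither quantity.
- s = 0.25, d = 0.05: 0.25 × 0.05 = 1.25 percentage points.
- s = 1, d = 0.20: 1 × 0.20 = 20 percentage points.
- Between arms A and B with the same s, the bias is s × (dA − dB). If cueing is the same in both arms it cancels; only arm-specific cueing distorts the comparison.

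**The case against.** The strongest reply is that Sections 6.3 and 8.4 do not conflict. The blind is defined with site pharmacists excepted, so an injecting pharmacist is within the definition, and participants and other staff remain blinded. That stands. A reader might infer that a site using the option is no longer running a double-blind administration; the documents do not support that. Disclosure to a participant is already contrary to the protocol, because Section 6.2 requires assignments to be kept secure and Section 6.3 makes even early leavers wait for unblinding. What is missing is separation of roles, not a duty of confidentiality.

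A reader might also argue that, because randomisation is stratified by country and not by site, differences in who injects are confounded with arm. They are not: assignment is still randomised, and differing injectors by themselves add variability. Bias needs arm-specific behaviour, of which the documents give no evidence.

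Nor should all 96 × 5 = 480 vaccination visits be counted as directly exposed. At 96 × 2 = 192 of them (Months 0 and 1) every blinded arm receives the same product.

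The primary endpoint names severe reactions, and these were rare in HVTN 100. Section 4.11.1.1, in blinded data that include placebo, reports severe systemic reactions in 4 participants (2%), and severe pain or tenderness in 1 participant for left-arm and 2 for right-arm injections. Cueing may move few severe reports. This limits the effect on that endpoint but not on the Kruskal-Wallis comparison, which uses all grades.

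Finally, the option needs both legal authority and a site's choice, so uptake may be zero. The Study Specific Procedures and pharmacy guidelines, which are not part of these documents, may already restrict it.

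**Conclusion.** The point holds as a gap in Section 8.4. Nothing in the plan separates an unblinded injector from the participant, or from the reactogenicity assessment, in Groups 1, 2 and 4. It is a risk of cueing in a tested safety comparison, not a failure of the blind as defined.

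Its ceiling is 96 participants and 192 arm-specific injections within primary objective 3, or 288 including Month 12. Its floor is zero, because the number of sites using the option is not given. No effect size can be derived from the documents. The antibody endpoints and open-label Group 3 are not affected.

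The conclusion rests on reading Section 6.3 as excepting all site pharmacists, and on no further restriction in documents not available here. It is best treated as a cheap improvement.

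**What to change.** Amend Section 8.4 and the Study Specific Procedures: in Groups 1, 2 and 4, nobody who prepared the dose or has access to assignments gives the protein injection or makes any of the reactogenicity assessments in Table 9-1. The pharmacist option remains for Group 3.

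Where a site has no other authorised injector, the minimum should be:
- bar the pharmacist from reactogenicity assessments;
- extend the Section 6.3 discussion ban to participants;
- record who gave each injection, so that reactogenicity can be re-examined by type of injector in a sensitivity analysis.

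The cost is a few sentences and, at some sites, the loss of a convenience. Those sites must use another authorised clinic injector, and the documents do not show whether that needs extra staff. Barring the pharmacist from the assessments costs almost nothing.
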